5.3 Sample Size

This is a randomized, controlled, double-blind, multicenter, superiority-designed phase III clinical study. Assuming that a PFS hazard ratio (HR) of HS-10296 to gefitinib is 0.67 (median PFS will be improved from 10 months to 15 months if the data meet the exponential distribution and statistical model meets the proportional hazard assumption), with the randomization ratio of 1:1, an enrollment duration of 8 months, a maximum observation period of 23 months after the first patient is enrolled, a two-sided alpha of 0.05, and with a power of 90% to detect the statistical differences between the two groups based on 262 events, approximately 410 patients need to be enrolled. The sample size is calculated by nQuery Advisor 8.0 software.

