12.3.3 Safety Analysis

12.3.3.1 Adverse Event

AEs occurring from treatment initiation until 28 days after the last dose will be summarized in the safety evaluation. AEs that occur prior to the initiation of study treatment and those occurring 28 days after the last dose will not be included in the summary table of AEs.

Adverse events occurring post-dose will be summarized by treatment group, mainly including:

- 1) The number and proportion of patients with at least one AE;
- 2) The number and proportion of patients with at least one study drug-related AE;
- 3) The number and proportion of patients with at least one AE of higher severity (CTCAE Grade ≥ 3);
- 4) The number and proportion of patients with at least one study drug-related AE of higher severity (CTCAE Grade ≥ 3);
- 5) The number and proportion of patients with at least one SAE;
- 6) The number and proportion of patients with dose modifications due to AEs;
- 7) The number and proportion of patients who have withdrawn from the study due to AEs;
- 8) The number and proportion of patients who died due to AEs.

Adverse events will be summarized by system organ classes and preferred terms. All adverse events will be tabulated.

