### **3.8. Subject Exposure and Medication Compliance**

Exposure to and compliance with the investigational drug are summarized based on the safety set by treatment group.

Exposure time is calculated as follows:

Total exposure time (days) = (date of last dose - date of first dose) + 1;

Cumulative exposure time (days) = total exposure time - cumulative number of days without medication;

Medication compliance = cumulative exposure time / total exposure time \* 100%;

The details of subject medication are listed.

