### 5.1. Adverse events

Adverse events will be coded with MedDRA 23.0 or a higher version.

CTCAE (4.03) will be obtained for the rating of the seriousness of adverse events. AEs that occur from the start of treatment to within 28 days after the last treatment will be summarized in the safety evaluation. AEs occurring prior to treatment initiation and AEs occurring within 28 days after the last treatment are tabulated separately and will not be included in summary tables for AEs.

General principles to follow when summarizing adverse events:

- 1) Adverse events are summarized by treatment group and system organ class/preferred time (SOC/PT).
- 2) If the same subject has the same adverse event multiple times, the one with the highest correlation with the investigational drug will be used to summarize the investigational drug-related AE and the one with the highest severity will be used for the summary of adverse event seriousness.
- 3) Only adverse events during the randomized, double-blind treatment stage and not during the cross-treatment stage are included.

All of the AEs of each subject will be presented in a list.

Related to the investigational drug refers to “definitely related,” “possibly related,” and “unable to be determined.”

Serious adverse events will be summarized and tabulated individually.

The following summary results will be given:

- 1) Summary of all adverse events
- 2) All adverse events summarized by system organ class and preferred term
- 3) Investigational drug-related adverse events summarized by system organ class and preferred term
- 4) All common adverse events summarized by system organ class and preferred term
- 5) All common investigational drug-related adverse events summarized by system organ class and preferred term
- 6) Adverse events of CTCAE grade  $\geq 3$  summarized by system organ class and preferred term
- 7) Investigational drug-related adverse events of CTCAE grade  $\geq 3$  summarized by system organ class and preferred term
- 8) Serious adverse events (SAEs) summarized by system organ class and preferred term
- 9) Investigational drug-related serious adverse events (SAEs) summarized by system organ class and preferred term
- 10) Adverse events leading to permanent discontinuation summarized by system organ class and preferred term
- 11) Investigational drug-related adverse events leading to permanent discontinuation summarized by system organ class and preferred term

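### Adverse events are compared by crude percentages only, although the design inputs imply about 20% longer progression-free treatment on HS-10296; a supplementary time-to-first-event summary would be a cheap improvement

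*SAP*

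**What the plan says.** - **Objective.** Protocol 5.1.2 and SAP 1.1.2 make comparing the safety of the two treatments a secondary objective.
- **AE measure.** Protocol 12.3.3.1 lists its summaries as patient counts and proportions, starting with "The number and proportion of patients with at least one AE". SAP 5.1 follows: "Adverse events are summarized by treatment group and system organ class/preferred time (SOC/PT". SAP 2.2.1 presents categorical variables as frequency and percentage.
- **Planned output.** SAP section 7 lists AE Tables 14.3.1.1 to 14.3.1.27. No title names a rate per unit of time, a time to onset or a cumulative incidence.
- **Exposure.** SAP 3.8: "Exposure to and compliance with the investigational drug are summarized based on the safety set by treatment group". The result goes into Table 14.1.7.1. Exposure is not used as a time base for any AE table.
- **Treatment length.** Protocol 6.1 continues treatment until investigator-assessed progression, or until withdrawal or discontinuation criteria are met. It may continue beyond progression if the investigator sees benefit.
- **Design assumption.** Protocol 5.3: "median PFS will be improved from 10 months to 15 months if the data meet the exponential distribution".

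**The concern.** When patients are treated to progression and one drug is expected to delay progression, patients on that drug are observed for AEs for longer. A crude percentage then mixes how often an event arises with how long the patient was at risk. If the trial meets its efficacy assumption, two drugs with the same hazard for a recurring type of event would not show the same percentage: HS-10296 would look worse. Conversely, equal percentages could conceal a lower hazard on HS-10296. The exposure table shows that treatment time differs, but a reader cannot use it to correct an individual preferred-term row, because time to first event is not tabulated.

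**Working it through.** **Inputs** (Protocol 5.3, repeated in SAP 1.2.3): "a PFS hazard ratio (HR) of HS-10296 to gefitinib is 0.67"; medians of 10 and 15 months, exponential; 1:1 allocation; 8 months of enrollment; 23 months in total; "a two-sided alpha of 0.05"; "with a power of 90% to detect the statistical differences between the two groups based on 262 events"; about 410 patients.

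**Assumptions added here:** uniform accrual, so follow-up C is uniform on 15 to 23 months; no dropout; treatment ends at progression or cut-off. Protocol 12.2 keeps AEs on post-progression treatment out of the summary tables, so progression-free time is a fair proxy for time at risk in those tables.

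**Step 1: reproduce the plan's figures.**
- Events (Schoenfeld): 4 × (1.960 + 1.282)² / (ln 0.67)² = 262.05, which rounds up to 263. Power at 262 events is 0.8999. The stated 262 is reproduced.
- Hazards: λ = ln 2/10 = 0.0693 and ln 2/15 = 0.0462 per month.
- Event probabilities, the mean of 1 − exp(−λC): 0.729 and 0.582, average 0.655. Then 262/0.655 = 400 patients, against about 410 stated. The model is close to the sponsor's.

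**Step 2: mean progression-free treatment time**, the mean of (1 − exp(−λC))/λ.
- Gefitinib: (1 − 0.271)/0.0693 = 10.5 months.
- HS-10296: (1 − 0.418)/0.0462 = 12.6 months.
- Ratio: 1.198.

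Sensitivity of the ratio:

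| Change | Ratio |
|---|---|
| 28-day post-treatment window added to both arms | 1.18 |
| Equal non-progression discontinuation, 0.005 to 0.02 per month | 1.19 to 1.18 |
| Cut-off at 16 months from first patient | 1.13 |
| Cut-off at 31 months | 1.26 |
| Cut-off at 36 months | 1.30 |

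**Step 3: crude percentages at an equal constant AE hazard r**, the mean of r/(r+λ) × (1 − exp(−(r+λ)C)).

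| r per month | Gefitinib | HS-10296 | Ratio |
|---|---|---|---|
| 0.0103 | 10.0% | 11.9% | 1.19 |
| 0.0369 | 30.0% | 35.1% | 1.17 |
| 0.0793 | 50.0% | 57.1% | 1.14 |

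The true hazard ratio is 1 in every row. In reverse, equal crude percentages of 10%, 30% or 50% would mean a hazard on HS-10296 that is 17%, 19% or 21% lower.

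**Step 4: equal hazards confined to the first 2 months**, r/(r+λ) × (1 − exp(−2(r+λ))).
- r = 0.1 per month: 17.0% versus 17.3%, crude ratio 1.02.
- r = 0.5 per month: 59.7% versus 60.8%, crude ratio 1.02.

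**Step 5: how two possible supplements behave.**
- *First-event rate per time at risk.* Under a constant hazard the ratio is 1.0, as it should be. With the early hazard of 0.1, mean time at risk to first event is 8.77 versus 10.48 months, so the rates are 0.1697/8.77 = 0.0193 and 0.1734/10.48 = 0.0165 per month: ratio 0.86. At r = 0.5 it is 0.87. The rate shows an advantage for HS-10296 that does not exist.
- *Kaplan-Meier probability at a fixed time.* Constant hazard 0.0103: 1 − exp(−0.0103 × 12) = 11.6% at 12 months in both arms. Early hazard 0.1: 1 − exp(−0.1 × 2) = 18.1% in both arms at any time after month 2. It gives the right answer in both cases, if censoring at treatment end is non-informative.

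**The case against.** The strongest case against has four parts.

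- **The crude proportion is legitimate.** The share of patients with an event during assigned treatment is a valid descriptive quantity, pre-specified in the protocol and followed by the SAP. No AE test, margin or decision rule is planned. A reader might infer that the safety comparison is statistically biased or invalid; the documents do not support that, because no AE inference is planned that could be biased. This part stands and limits the severity.
- **The imbalance is visible.** Exposure is reported by arm, and laboratory, vital sign, ECG and LVEF results are summarized by visit, which aligns time across arms. This stands for those data. It does not let a reader adjust AE rows.
- **The 20% is not in the plan.** A reader might say that the design assumes 20% longer exposure. It does not: the documents assume median PFS, and the 20% is derived, under uniform accrual and no dropout, and moves with the cut-off. This stands.
- **The obvious remedy can mislead.** A reader might conclude that dividing by exposure settles the matter. For early-onset events the crude percentages are nearly right, and the rate would flatter HS-10296 (ratio 0.86). The documents give no AE onset times, so it is unknown which case applies to which event. In addition, total exposure in SAP 3.8 runs to the last dose with no stop at progression or crossover, so it is not the time at risk for the AE tables. This stands, and it determines the form of the fix.

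What remains is that the AE tables pool events over the whole treatment period, and nothing in the documents confines those events to early treatment.

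**Conclusion.** The point holds as a low-severity, cheap improvement. The design inputs imply about 20% longer mean progression-free treatment time on HS-10296 (12.6 versus 10.5 months), given uniform accrual, no dropout and treatment ending at progression or cut-off. For events that keep arising at an equal constant hazard, crude percentages on HS-10296 would be higher by about 2 points at 10%, 5 points at 30% and 7 points at 50%. For events confined to the first 2 months the difference is 0.4 points at 17% and 1.1 points at 60%. The consequence is for the reading of side-by-side percentages under a comparative safety objective. It does not reach the primary analysis or any planned test.

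**What to change.** Keep the crude tables. In SAP 5.1, pre-specify a supplementary time-to-first-event analysis by arm, as follows.

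- **Events:** any AE, grade 3 or higher, serious AE, AE leading to discontinuation, and common preferred terms.
- **Summary:** Kaplan-Meier event probabilities at fixed times, for example 3, 6 and 12 months, with 95% CI, censored at the end of the AE inclusion window.
- **Optional:** first-event rates per 100 patient-years at risk, with a note that they assume a constant hazard and would favour HS-10296 for early-onset events.
- **Time at risk:** from first dose to first event or the end of the AE inclusion window, excluding post-progression treatment and crossover. Do not use total exposure from SAP 3.8. Protocol 12.2 keeps AEs on post-progression treatment out of the summaries; SAP 5.1 mentions only crossover and should say the same.
- **Reconcile first:** Protocol 12.2 and SAP 5.1 each say both that AEs in the 28 days after the last dose are summarized and that they are kept out of the summary tables. The window cannot be fixed until this is settled.

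The cost is a few extra tables, using AE start dates and dosing dates that are already collected, and an assumption that censoring at treatment end is non-informative, which should be stated.

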## 5.2. **Laboratory testing**

In accordance with the study protocol, laboratory testing was performed during specific visit periods in this study. For the specific examination items, refer to [Section 1.3.3](#).

Laboratory test data will be divided into continuous variables and categorical variables, which will be analyzed by group as follows:

- 1) For quantitative results, the actual measurements and their change from baseline will be descriptively summarized by visit;
- 2) For qualitative results, the results for the judgment of the clinical significance of the laboratory test data and the numbers and ratios of subjects with clinically significant abnormalities by visit will be presented in cross table form.
- 3) For qualitative results, the numbers and ratios of subjects with results that were normal or abnormal without clinical significance at baseline but turned abnormal with clinical significance after treatment are summarized.

All laboratory test data and the results for the judgment of clinical significance are presented in list form.

## 5.3. **Vital Signs**

The measurement results and changes versus baseline of each vital sign indicator during each visit are summarized and described by treatment group, including temperature (oral temperature, ear temperature, or axillary temperature, expressed in degrees Celsius), blood pressure (systolic and diastolic pressure), pulse (heart rate per minute), respiratory rate, and weight.

All vital sign check results, weight, and ECOG PS scores are listed separately.

## 5.4. **Physical Examination**

All physical examination results are given in lists.

## 5.5. **12-lead ECG**

Because each ECG examination in this study is repeated 3 times, the average ECG results of each examination serve as the ECG values for the examination in the following analysis:

- 1) The changes versus baseline of various ECG indicators (heart rate (beats/minute), PR

(ms), QRS duration (ms), RR interval (ms), QT, and QTcF (ms)) at each visit and each post-treatment visit are summarized by treatment group and visit.

- 2) The proportions of  $\leq$  450 ms, 450-480 ms, 480-500 ms, and  $>$  500 ms are described for the absolute values at baseline and during post-treatment visits of QT interval and QTcF interval by treatment group and visit and the proportions of change versus baseline during post-treatment visits at  $\leq$  30 ms, 30-60 ms, and  $>$  60 ms are given.
- 3) The changes versus baseline in the clinical significance of the 12-lead ECG examination results (normal, abnormal without clinical significance, and abnormal with clinical significance) are summarized with cross tables by visit and treatment group.

A list is made of all of the ECG examination results.

“Abnormal and clinically significant” above is an EDC-collected value.

#### **5.6. LVEF measured with echocardiography or MUGA**

The following will be summarized by treatment group at each visit and after treatment:

- Summary of the proportion of subjects with LVEF value  $<$  50% and decrease versus baseline  $\geq$  10%
- Summary of the proportion of subjects with LVEF value  $\geq$  50% and decrease versus baseline  $\geq$  15%.

All LVEF results of each subject will be presented by list.

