5.2.2 Safety Endpoints

Occurrence of adverse events; occurrence of serious adverse events; proportion of patients withdrawn from the study due to adverse events; laboratory test result changes (blood chemistry, hematology, and urinalysis); changes in vital signs, physical examination, body weight, 12-lead electrocardiogram (ECG), left ventricular ejection fraction (LVEF), ECOG performance status (PS) score, and ophthalmic examination.

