9.1.2.2 Treatment Visits (C1 to C7 +, D1 to D127 +)

Treatment Visits (C1 to C7, D1 to D127)

- Treatment visits will be performed on the first day of the first 7 treatment cycles (C1 to C7) (CnD1, n = 1 to 7), with the exception of C1D1, and two additional visits will be added on C1D8 and C1D15, respectively. The specific visit procedures are as follows:
 - The investigational product will be dosed once daily
 - Full physical examination, body weight examination, ECOG PS score, vital signs, laboratory tests (clinical chemistry, hematology, and urinalysis), and 12-lead ECG will be performed every 3 weeks (CnD1)
 - Two additional tests will be added on C1D8 and C1D15: including vital signs, laboratory tests (clinical chemistry, hematology, and urinalysis), and 12-lead ECG
 - Ophthalmic examinations will be performed as clinically indicated throughout the treatment period, and the specific items will be determined by the investigator or specialist depending on the patient's condition
 - Echocardiography will be performed every 12 weeks from the first dose (and as clinically indicated)
 - Response evaluations in solid tumors will be performed per RECIST 1.1 every 6 weeks
 - The adverse events and concomitant medications will be recorded

Treatment Visits (C7 +, D127 +)

Treatment visits after Cycle 7 will be performed according to the following procedures:

- The investigational product will be dosed once daily
- Full physical examination, body weight examination, ECOG PS score, vital signs, laboratory tests (clinical chemistry, hematology, and urinalysis), and 12-lead ECG will be performed every 6 weeks (C1 to C21) or every 12 weeks (C23 and thereafter)
- Ophthalmic examinations will be performed as clinically indicated throughout the treatment period, and the specific items will be determined by the investigator or specialist depending on the patient's condition

- Echocardiography will be performed every 12 weeks (and as clinically indicated)
- Response evaluations in solid tumors will be performed per RECIST 1.1 every 6 weeks (C1 to C21) or every 12 weeks (C23 and thereafter)
- The adverse events and concomitant medications will be recorded

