### 1.3.3. Safety Evaluation Indicators

The safety endpoints include:

- 1) Adverse events and serious adverse events
- 2) Laboratory testing
  - Clinical blood biochemistry: Albumin, ALT, AST, alkaline phosphatase, bilirubin, total bilirubin, calcium, total blood calcium, creatinine, creatine kinase, glucose, LDH, HbA1C, magnesium, potassium, sodium, urea nitrogen or urea (pick one of two)
  - Hematology: Hemoglobin, white blood cells, hematocrit, red blood cell count (RBC), absolute white blood cell count (neutrophils, lymphocytes, monocytes, basophils, eosinophils), platelet count, reticulocyte count
  - Urinalysis: Glucose, urine protein, blood in urine
- 3) Vital signs: Pulse, sitting systolic and diastolic blood pressure, respiratory rate, and body temperature.
- 4) Physical examination: Including general condition, skin and mucous membranes, lymph nodes, head, neck, chest, abdomen, spine, and limbs or other examinations.
- 5) Weight
- 6) 12-lead electrocardiogram (ECG): Heart rate (beats/minute), QRS duration (ms), PR interval (ms), RR interval (ms), QT and QTcF intervals (ms), and clinical classification of normal/abnormal ECG.
- 7) ECOG Performance Status Score
- 8) LVEF Measured With Echocardiography or MUGA
- 9) Changes of ophthalmological examination

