### 2.2.7. Definition of baseline

Unless specifically indicated, the baseline values of the effectiveness endpoints of this study are defined as the last valid measurement of the endpoint before randomization. The baseline values of safety endpoints are defined as the last valid measurement before the first use of the investigational drug, including the day of medication.

Change from baseline will be calculated based on the measurement after baseline minus the measurement at baseline, or measurement after baseline - measurement at baseline.

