14.3.5 LVEF	Table 14.3.5.1 Summary of LVEF abnormalities by visit-safety set Table 14.3.5.2 Summary of LVEF abnormalities after treatment-safety set
14.3.6 Physical examination	Table 14.3.6.1 Cross table of physical examination results before and after treatment-safety set Table 14.3.6.2 Summary of normal or abnormal [tests] without clinical significance at baseline that turned to abnormal with clinical significance after treatment (physical examination)-safety set

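### LVEF, a named safety endpoint measured every 12 weeks, gets only two threshold proportions and a listing: no summary of values or change from baseline, and no statement whether the decreases are absolute or relative

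*SAP*

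**What the plan says.** Protocol 5.2.2 counts changes in "left ventricular ejection fraction (LVEF), ECOG performance status (PS) score, and ophthalmic examination" among the safety endpoints, and SAP 1.3.3 repeats it as "LVEF Measured With Echocardiography or MUGA". Comparing safety between the arms is a secondary objective in both documents. The schedule is regular: "Echocardiography will be performed every 12 weeks from the first dose" (Protocol 9.1.2.2), with further examinations at screening and at discontinuation.

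SAP 5.6 plans three outputs for LVEF, the first two each introduced as "Summary of the proportion of subjects with LVEF value":
- the proportion with LVEF below 50% and a decrease from baseline of at least 10%;
- the proportion with LVEF of 50% or above and a decrease of at least 15%;
- a listing: "All LVEF results of each subject will be presented by list".

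The table list in SAP section 7 matches. Under 14.3.5 it has "Table 14.3.5.1 Summary of LVEF abnormalities by visit-safety set" and a companion table of abnormalities after treatment, and nothing else. Protocol 12.3.3 has no LVEF subsection.

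Other continuous safety measures are treated differently. SAP 5.2 and 5.3 summarise laboratory values and vital signs, with change from baseline, by visit. SAP 5.5 does so for ECG ("The changes versus baseline of various ECG indicators") and gives threshold categories as well.

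**The concern.** LVEF is continuous, is measured repeatedly on both arms, and is the protocol's only scheduled measure of ventricular function. Two cut-offs record only large individual falls. If one drug lowered LVEF a little in most patients, few would cross a cut-off, and the planned tables could look similar on both arms. A mean-change analysis made later from the listing would not be pre-specified.

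There is a second, separate problem. LVEF is itself a percentage, so a decrease of 10% or 15% can mean percentage points or a fraction of the baseline value. SAP 5.6 does not say which, and two programmers could produce different tables from the same data.

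**Working it through.** **Plan's own figure.** The documents state no LVEF mean, SD, expected rate or test. The only figure borrowed is the sample size: about 410 patients at 1:1, so 410 / 2 = 205 per arm.

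**Step 1: is a change table planned anywhere?** SAP 2.2.1 says which statistics describe a continuous variable. SAP 2.2.6 assigns LVEF to analysis visit windows. SAP 2.2.7 defines change ("Change from baseline will be calculated based on the measurement after baseline minus the measurement at baseline"). SAP 2.2.9 mentions descriptive summaries of safety variables by visit window. None of these orders an LVEF output, and neither SAP 5.6 nor list 14.3.5 contains one. The definitions exist; the table does not.

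**Step 2: does the reading of the decrease matter?**

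| Baseline to later value | Points | Relative | Counted if points | Counted if relative |
|---|---|---|---|---|
| 60% to 51% | 9 | 9/60 = 15% | no | yes (second category) |
| 52% to 46% | 6 | 6/52 = 11.5% | no | yes (first category) |

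SAP 2.2.7 leans towards points, but SAP 5.6 does not state it.

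**Step 3: how much information do the categories lose?** Power is used here only as a yardstick, because the SAP plans no LVEF test. *Assumptions, not in the documents:* baseline mean 64, SD 5; SD of change σ = 5, 6 or 8 points; a mean fall δ on one arm and none on the other; 205 measured per arm; two-sided 0.05.

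Change scale, one scan: power ≈ Φ(δ / (σ√(2/205)) − 1.96), with √(2/205) = 0.0988. For δ = 2:
- σ = 5: 2/0.494 = 4.05; Φ(2.09) = 98%
- σ = 6: 2/0.593 = 3.37; Φ(1.41) = 92%
- σ = 8: 2/0.790 = 2.53; Φ(0.57) = 72%

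Categories: simulation under the same model, with Fisher's exact test on meeting either category. The four-scan rows count any occurrence and assume a within-patient correlation of 0.5.

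| Mean fall, reading | Scans | Categories (σ = 5/6/8) | Change scale, one scan (σ = 5/6/8) |
|---|---|---|---|
| 2 points, absolute | 1 | 8% / 16% / 21% | 98% / 92% / 72% |
| 2 points, absolute | 4 | 34% / 43% / 40% | as above |
| 3 points, absolute | 1 | 27% / 43% / 44% | 100% / 100% / 97% |
| 3 points, absolute | 4 | 77% / 82% / 82% | as above |
| 3 points, relative | 1 | 78% / 77% / 68% | as above |
| 5 points, absolute | 1 | 90% / 94% / 92% | about 100% |

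Repeat simulations move individual entries by a few percentage points. Across runs, the 2-point absolute case spans about 6–44% for the categories and 71–100% for change.

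To see why: with σ = 6 and a 2-point fall, the combined category rate is 4.1% against 2.0%. That is 0.041 × 205 = 8.4 subjects against 0.020 × 205 = 4.1, a difference of about four subjects.

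**The case against.** The strongest reply has four parts.

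1. **Nothing is hidden.** Every LVEF value is listed, and clinically significant abnormalities are reported as adverse events and tabulated by arm. This stands against any claim that a fall would go unseen. It does not supply a summary by arm.

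2. **A single-scan calculation understates the plan.** Patients are scanned repeatedly, and the after-treatment table can draw on every scan. This stands: with four scans the categories reach 77–84% power for a 3-point fall. The material loss is at about 2 points, and the documents do not say whether a fall of that size matters clinically.

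3. **Power is the wrong yardstick for a descriptive section.** This is fair, so the figures are used only to measure information lost. A between-arm difference with a confidence interval also goes beyond what the SAP gives laboratory tests, vital signs or ECG. The by-visit change table does not.

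4. **The general rules in SAP 2.2.1 and 2.2.9 permit an LVEF summary.** They permit one but do not commit to it.

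A reader might also infer that the categories miss dangerous falls below a 40% floor, for example 45% to 36%. The documents do not support that as a headline. An LVEF of 40% or lower is an entry exclusion, and no on-treatment limit is set. The example is a 9-point fall, not counted in points, but it is 9/45 = 20% relative and then counted. The gap affects only patients who enter below 50%. Under the assumed baseline this is Φ((50 − 64)/5) = Φ(−2.8) = 0.26%, or about one of 410 patients.

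**Conclusion.** The point holds as an omission and an ambiguity in the safety reporting. A named endpoint has no planned summary of values or change, unlike the comparable safety measures, and the two category definitions can be read in two ways.

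The size rests on assumed LVEF variability. For a mean fall of about 2 points on one arm, with decreases in points, the categories have roughly 6–44% power against 71–100% on the change scale. The loss shrinks for 3-point falls when several scans count, and shrinks again if decreases are relative. At about 5 points the categories show the fall even with one scan. It would be wrong to conclude that a real decline must go unnoticed, or that the advantage of the change scale is large in every scenario. The primary PFS analysis is unaffected.

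**What to change.** In SAP 5.6:
- Keep the two threshold categories, and state whether the 10% and 15% decreases are absolute percentage points or relative to baseline.
- Add a summary of LVEF and change from baseline by visit and arm (n, mean, SD, median, minimum, maximum).
- In the same table, add the worst post-baseline change per subject, with the between-arm difference and 95% CI labelled as descriptive.

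List this as one new table under 14.3.5. A separate category at 40% is not needed.

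The cost is one extra table and a little programming. The data are already collected, the visit windows and the definition of change already exist in SAP 2.2.6 and 2.2.7, and no new examinations are required.
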